6.13.3. Adverse events

In order to assign AEs into the different Analysis Periods, the following algorithms are applied.

6.13.3.1. Treatment-emergent AEs

Safety data with missing or partial onset dates/times (Adverse Events) are handled as follows:

For AEs reported during the core study as well as AEs between the core EOT date + 15 days and the first treatment in the extension, these variables are used as derived in the core study, and are not re-derived for the analysis of the Combined Analysis Period.

For AEs reported on the "Adverse Event" page for the extension study the following rules are applied:

- Onset day missing: If month and year is clearly on or after date of first study drug intake in the extension study month and year, and clearly before or on the month and year of minimum of (EOS, last intake date + 15 days), the event is considered to be treatment-emergent. For pregnancy interruptions, if month and year is clearly on or after date of first study drug intake in the extension study month and year and clearly before the last study drug intake date prior to pregnancy interruption + 15 days, or clearly on or after the re-initiation date of study treatment after planned pregnancy and prior to or on the minimum of [EOT date + 15 days, cut-off date], the event is considered to be treatment-emergent.
 - If the month and year correspond to month and year of date of first study drug intake (in the extension study), impute onset date and time as the date and time of the first study drug intake in the extension study. If the date/time of first study drug intake (in the extension study) is missing, then use enrollment date/time.
 - If the month and year are clearly after date of first study drug intake in the extension study month and year, but a date of re-initiation with corresponding month and year is documented, impute onset date and time as the date and time of this re-initiation study drug intake (if more than one study drug re-initiations are documented in this month and year, impute with the date and time of the earliest of those).
 - If the month and year are clearly after date of first study drug intake in the extension study month and year, but no date of re-initiation with corresponding month and year is documented, the onset date is imputed to the first day of the month and year given, and time to 00:00.
 - If neither date of first study drug intake in the extension study nor extension enrollment date are available, or if event onset month and year is clearly prior to the date of first study drug intake in the extension study month and year (or, if missing, the enrollment month and year), the onset date is imputed to the last day of the given month (i.e., 28th, 29th, 30th, or 31st, depending on the month) and year, and time is imputed to 00:00.

- Onset day and month missing: If the year is the same year as the year of first study drug intake in the extension study or later, and if the year is prior to or in the same year as the minimum of (cut-off date, last intake date + 15 days), the AE is considered to be treatment-emergent. For pregnancy interruptions, if the year is the same year as the year of first study drug intake in the extension study or later, and if the year is prior to or in the same year as the minimum of (cut-off date, last intake date + 15 days), the AE is considered to be treatment-emergent. If the year corresponds to the year of first study drug intake (in the extension study), impute onset date and time as the date and time of the first study drug intake in the extension study. If first study drug intake (in the extension study) is missing, then use enrollment date/time.
- If the year is clearly after the year of first study drug intake in the extension study, but a date of re-initiation with corresponding year is documented, impute onset date and time as the date and time of this re-initiation study drug intake (if more than one study drug re-initiations are documented in this year, impute with the date and time of the earliest of those).
- If the year is clearly after the year of first study drug intake in the extension study, but no date of re-initiation with corresponding year is documented, the onset date is imputed to 1 January of the given year and time to 00:00.
- If neither date of first study drug intake in the extension study nor extension enrollment date are available, or if the event onset year is clearly prior to the year of first study drug intake (or, if missing, year of enrollment), the onset date is imputed to 31 December of the given year and time is imputed to 00:00.
- Missing onset time is imputed to:
 - the time of the first study drug intake in the extension study, if the onset date equals the date of first study drug intake in the extension study.
 - the time of the study drug intake at re-initiation in the extension study, if the onset date equals the date of a documented study drug re-initiation.
 - 00:00, for any other onset date.
- Onset date is completely missing: considered to be treatment-emergent. The onset date and time are imputed as date and time of the first study drug intake in the extension study.

AEs with missing or partial onset date may be considered to be treatment-emergent as per the definitions above. However, they are not considered to be "Day 1" AEs and will not appear in summaries of AEs on Day 1.

For AEs reported on the "Ongoing Adverse Events from AC-058301" eCRF page for the extension study, no dates are imputed and the events are considered to be not treatment-emergent with respect to the Extension Analysis Period.

6.13.4. Study treatment start and EOT date

The following imputations of study treatment start and extension EOT date are considered for assigning safety events and assessments to the treatment-emergent period and used for deriving efficacy variables with definitions requiring extension EOT date. It is not considered for derivation of exposure variables.

Type of date/time	Date/time is incomplete	Date/time is missing
Study treatment start date	Maximum of lower limit and randomization/enrollment date.	Randomization/enrollment date
Study treatment start time	See missing.	0:00 or randomization time if study treatment start date (after imputation) is equal to randomization/enrollment date.
Extension EOT date	Earliest among the upper limit, date of first commercial ponesimod intake in CM dataset -1, and EOT visit date -1.	Earliest among the upper limit, date of first commercial ponesimod intake in CM dataset -1, and EOT visit date -1

6.13.5. Treatment exposure

Exposure data is entered as intervals on the eCRF with an exposure start and end date.

If both the start and end date of any interval is completely missing no date will be imputed.

6.14. Appendix 14 PRO and other composite assessment scoring and handling of missing data

6.14.1. MSFC

A more comprehensive description of the test and its administration is provided in the protocol appendix 6. The MSFC score will be calculated as the mean of the Z-scores of the 3 components:

- (1) Timed 25-Foot Walk (T25FW)
- (2) 9-Hole Peg Test (9-HPT)
- (3) Paced Auditory Serial Addition Test (PASAT-3).

for each of the scheduled assessment visit using the following equation (MSFC administration and scoring manual, Fisher *et al.*, 2001, National MS society).

$$\text{MSFC Z-score}_t = \frac{Z_{\text{arm, average }t} - Z_{\text{leg, average }t} + Z_{\text{cognitive }t}}{3}$$

In more details the score will be calculated as follows:

Where t = time, baseline mean and SD refer to the mean and standard deviation in the study independent of treatment arm (FAS) at baseline.

The average (1/9-HPT) and average T25FW are derived as follows.

Average 1/9-HPT=
$$[1/Mean trials arm left + 1/mean trials arm right]/2$$

Average T25FW = mean of trials (i.e. trial 1 and trial 2) = $(trial 1 + trial 2)/2$

For the T25FW and 9-HPT, a higher raw score represents deterioration whereas, for the PASAT-3 a lower raw score represents deterioration. After the transformation to Z-scores the negative values Z-scores of each of the components as well as the MSFC Z-score indicate deterioration in the neurological function.

The subcomponents are considered in addition separately. These are: Average T25FW in seconds, PASAT-3 score in number correct, and the Average 9-HPT in seconds. The Average 9-HPT is defined as Average 9-HPT = mean (Mean trials arm left, mean trials arm right).

Handling of missing data for MSFC analysis

For assessments 9-HPT and T25FW, if only one trial is available that score is used instead of the mean, if more trials are available at the same visit the mean is derived based on all available trials.

For assessments 9-HPT, if only results from one arm are available, the reciproce is used for Average 1/9-HPT.

For overall composite MSFC score, if any of the three components is missing at that visit, the MSFC score is set to be missing, no imputation is conducted.

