1.1.2. Efficacy objectives and endpoints

- To describe the long-term disease control in subjects with RMS receiving ponesimod 20 mg.
- To describe the effect of a switch from teriflunomide to ponesimod 20 mg on disease control in subjects with RMS.

The tables below detail which endpoints will be analyzed for the Extension Analysis Period and for the Combined Analysis Period. See Section 5.1.1 for definitions of the Analysis Periods, and Section 5.1.5 for further details regarding the analysis strategy.

[#] The selection of AEs of special interest is based on the anticipated risks of treatment with ponesimod

AE = adverse event; AESI-adverse event of special interest; DBP = diastolic blood pressure; ECG = electrocardiogram; FEV₁ = forced expiratory volume in 1 second; FVC = forced vital capacity; HR = heart rate; QTcB = QT corrected for heart rate on the basis of Bazett's formula; QTcF = QT corrected for heart rate on the basis of Fridericia's formula; SAE = serious adverse event; SAP = statistical analysis plan; SBP = systolic blood pressure.

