5.3.2.5.3. Change in MSFC Z-score from baseline by visit up to Extension EOS

MSFC Z-score as well as its subcomponents scores and changes from core baseline will be descriptively summarized for each treatment group by visit on the EXTS. Mean change (\pm SE) over time will be graphically presented by treatment group. Same analysis relative to extension baseline will be done on the EXTS during extension period. A listing will be prepared.

5.3.2.5.4. Change in the SDMT score from baseline by visit up to Extension EOS

SDMT scores and change from baseline will be descriptively summarized for each treatment group by visit on the EXTS. Mean change (\pm SE) over time will be graphically presented by treatment group. Same analysis relative to extension baseline will be done on the EXTS during extension period. A listing will be prepared.

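### The one-arm 9-HPT rule in the MSFC ignores why the other arm is missing, so the change from baseline can understate a loss of arm function or show it as a gain.

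*SAP*

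**What the plan says.** SAP 6.14.1 builds the composite from three parts: "The MSFC score will be calculated as the mean of the Z-scores of the 3 components". The displayed formula is the arm Z-score, minus the leg Z-score, plus the cognitive Z-score, divided by 3. With both arms available, the arm part starts from half the sum "1/Mean trials arm left + 1/mean trials arm right". For standardisation, "baseline mean and SD refer to the mean and standard deviation in the study independent of treatment arm (FAS) at baseline"; the two values are not given.

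On direction, the section says: "For the T25FW and 9-HPT, a higher raw score represents deterioration". Because the 9-HPT enters as a reciprocal, a longer time lowers the arm Z-score, and a negative Z-score means worse function.

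The missing-data paragraph then gives the one-arm rule: "For assessments 9-HPT, if only results from one arm are available, the reciproce is used for Average 1/9-HPT". For the composite, "if any of the three components is missing at that visit, the MSFC score is set to be missing, no imputation is conducted". Neither rule separates a test that the subject could not perform from one not done for another reason. The section refers to protocol appendix 6 for a fuller description of the test and its administration.

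The score is used in SAP 5.3.2.5.3: "MSFC Z-score as well as its subcomponents scores and changes from core baseline will be descriptively summarized", by treatment group and visit on the EXTS, and again relative to the extension baseline.

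**The concern.** A 9-HPT result for one arm can be absent because the subject can no longer do the test with that arm. The absence then carries information about the disability being measured. Under the one-arm rule the remaining arm stands in for both. A subject whose weaker arm fails is scored as if both arms worked like the stronger one, while the baseline value still includes the weaker arm.

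The relevant objective is "To describe the long-term disease control in subjects with RMS receiving ponesimod 20 mg", over a 108-week core study followed by up to 240 weeks of extension treatment (288 in Ukraine). A rule that can turn a loss of function into a rise in the score works against that description, and it does so without any hypothesis test being involved.

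**Working it through.** The SAP states no figure on this point, so there is nothing to reproduce. The check applies its formulas to example subjects.

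**Inputs from SAP 6.14.1**
- Two arms with times a and b: A = (1/a + 1/b)/2.
- One arm with time x: A = 1/x.
- Change in arm Z-score = (A at follow-up − A at baseline)/SD. The baseline mean cancels.
- Change in MSFC = change in arm Z-score / 3, with walk and PASAT held constant.

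**Assumptions (not in the SAP)**
- The 9-HPT times in the table.
- SD of A between 0.006 and 0.012 per second.
- Comparator: an arm that cannot do the test has zero speed (reciprocal 0).

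**Worked case, 20 s and 25 s, the 25 s arm lost, the other unchanged**
- Baseline: (1/20 + 1/25)/2 = (0.050 + 0.040)/2 = 0.045.
- SAP follow-up: 1/20 = 0.050, a difference of +0.005. Arm Z-score: 0.005/0.012 = +0.42 to 0.005/0.006 = +0.83. MSFC: +0.14 to +0.28.
- Lost arm scored 0: (0.050 + 0)/2 = 0.025, a difference of −0.020. Arm Z-score: −1.67 to −3.33. MSFC: −0.56 to −1.11. With an illustrative 300 s limit in place of 0, the MSFC change is −0.51 to −1.02.

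**Other cases (MSFC change, SD 0.012 to 0.006)**

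| Baseline (s) | Follow-up | A before | A under SAP | SAP rule | Lost arm = 0 |
|---|---|---|---|---|---|
| 20/25 | 25 s arm lost, other 22 s | 0.0450 | 0.0455 | +0.01 to +0.03 | −0.62 to −1.24 |
| 20/25 | 25 s arm lost, other 24 s | 0.0450 | 0.0417 | −0.09 to −0.19 | −0.67 to −1.34 |
| 20/25 | 20 s arm lost, other 25 s | 0.0450 | 0.0400 | −0.14 to −0.28 | −0.69 to −1.39 |
| 22/22 | one arm lost, other 22 s | 0.0455 | 0.0455 | 0 | −0.63 to −1.26 |
| 20/40 | 40 s arm lost, other 20 s | 0.0375 | 0.0500 | +0.35 to +0.69 | −0.35 to −0.69 |

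**When the sign reverses.** The score rises when 1/x > (1/a + 1/b)/2, that is, when x < 2ab/(a + b), the harmonic mean of the baseline times. For 20/25 s this is 2 × 20 × 25/45 = 22.2 s; for 20/40 s it is 2 × 20 × 40/60 = 26.7 s. An unchanged faster arm is always below this value, and an unchanged slower arm is always above it. The sign does not depend on the SD.

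**Same-arm comparison, for an arm missing for reasons other than inability.** If the 20 s arm is unchanged, 1/20 − 1/20 = 0, against +0.14 to +0.28 under the SAP. If it slows to 24 s, 1/24 − 1/20 = −0.0083. Divided by the SD and by 3, this is −0.23 to −0.46, against −0.09 to −0.19 under the SAP. The mismatch therefore distorts the change even when the missing arm says nothing about disability.

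**The case against.** **Recording of inability.** Protocol appendix 6 is not shown. If inability is entered there as a limit value, the arm counts as available and the one-arm rule does not apply to it. This stands as a condition on the point. It does not remove it, because 6.14.1 applies to any missing arm, and the one-arm against two-arm mismatch remains for arms missing for other reasons.

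**Stronger readings.** A reader might infer that severe loss of function generally scores as improvement. It does not: reversal needs the remaining arm to be faster than the harmonic mean of the baseline times. A reader might also infer that badly disabled subjects vanish because the composite is set to missing when a component is missing. That goes too far. Their available subcomponents are still summarised and listed, and leaving an incomplete composite unimputed is a transparent choice. Nor does the SAP show that 9-HPT in seconds is biased in the same way, since it states no one-arm rule for that variable.

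**Consequence.** The MSFC is in Table 5 (other endpoints), all analyses are exploratory (Section 2), and disability is carried mainly by CDA and EDSS. EDSS is scheduled at every scheduled extension MSFC visit (Table 12). This stands and limits the priority.

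**Remedy.** Assigning a worst T25FW time, or classifying inability from EDSS/FS, is debatable. Section 5.1.3.2 keeps core baselines as derived, and re-deriving all core scores after the core study has been unblinded would be a real cost. This also stands; the fix below avoids those steps.

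**Conclusion.** The point holds for the one-arm 9-HPT rule. As written, it can turn the loss of the weaker arm into a gain (+0.14 to +0.28 MSFC units for 20/25 s, +0.35 to +0.69 for 20/40 s). In the other cases it understates the loss. For 20/25 s with the faster arm lost, the change is −0.14 to −0.28, against −0.69 to −1.39 with the lost arm scored 0.

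These are changes for one subject and rest on assumed times and an assumed SD. That losing the slower arm with the other unchanged raises the score follows from the formula alone, provided both arms were measured at baseline. The comparison with a score of 0 applies only where inability is recorded as no result.

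A reader might go on to infer a particular bias in the group means, or between early and delayed ponesimod. The SAP does not support a figure, because nothing in it says how many subjects have one arm only, or why. With a descriptive endpoint in the lower tier, the priority is low to moderate.

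**What to change.** In SAP 6.14.1:

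1. State how inability is recorded. Where it is recorded, let the arm that could not be tested because of physical limitation enter the average with reciprocal 0, or with the recorded limit value.
2. For an arm missing for any other or unknown reason, compute the change from baseline using the same arm at baseline, keeping the existing FAS baseline mean and SD, or set the arm Z-score to missing.
3. Present the current rule as a sensitivity analysis. Report by visit the number of subjects with one arm only and the number whose T25FW was not done because of inability.

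A worst-value imputation for T25FW, a classification by EDSS/FS and a re-derivation of all core scores are not required. If core visits keep their derived scores, a footnote in the Combined Analysis Period tables should say so.

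The cost is a few sentences and a little extra programming. The downside is that the score of a subject unable to do the test rests on an assigned value; the sensitivity analysis shows how much that matters.

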6.14.2. SF-36 analysis

6.14.2.1. SF-36 scoring

SF-36 scoring is performed via licensed vendor QualityMetric using PRO CORE software. The 36 questions are imported for processing and detailed process steps can be found in PRO CORE 1.4 manual.

The original SDTM QSTESTCD need to be transformed into imported test code requested by PRO CORE. Below are coding rules.

QSTESTCD	QSTEST	SF-36 coding for PRO CORE
SF36201	SF-36 v2.0 Standard-Question 1	GH01
SF36202	SF-36 v2.0 Standard-Question 2	HT
SF36203A	SF-36 v2.0 Standard-Question 3a	PF01
SF36203B	SF-36 v2.0 Standard-Question 3b	PF02
SF36203C	SF-36 v2.0 Standard-Question 3c	PF03
SF36203D	SF-36 v2.0 Standard-Question 3d	PF04
SF36203E	SF-36 v2.0 Standard-Question 3e	PF05
SF36203F	SF-36 v2.0 Standard-Question 3f	PF06
SF36203G	SF-36 v2.0 Standard-Question 3g	PF07
SF36203H	SF-36 v2.0 Standard-Question 3h	PF08
SF36203I	SF-36 v2.0 Standard-Question 3i	PF09
SF36203J	SF-36 v2.0 Standard-Question 3j	PF10
SF36204A	SF-36 v2.0 Standard-Question 4a	RP01
SF36204B	SF-36 v2.0 Standard-Question 4b	RP02
SF36204C	SF-36 v2.0 Standard-Question 4c	RP03
SF36204D	SF-36 v2.0 Standard-Question 4d	RP04
SF36205A	SF-36 v2.0 Standard-Question 5a	RE01
SF36205B	SF-36 v2.0 Standard-Question 5b	RE02
SF36205C	SF-36 v2.0 Standard-Question 5c	RE03
SF36206	SF-36 v2.0 Standard-Question 6	SF01
SF36207	SF-36 v2.0 Standard-Question 7	BP01
SF36208	SF-36 v2.0 Standard-Question 8	BP02
SF36209A	SF-36 v2.0 Standard-Question 9a	VT01
SF36209B	SF-36 v2.0 Standard-Question 9b	MH01
SF36209C	SF-36 v2.0 Standard-Question 9c	MH02
SF36209D	SF-36 v2.0 Standard-Question 9d	MH03
SF36209E	SF-36 v2.0 Standard-Question 9e	VT02
SF36209F	SF-36 v2.0 Standard-Question 9f	MH04
SF36209G	SF-36 v2.0 Standard-Question 9g	VT03
SF36209H	SF-36 v2.0 Standard-Question 9h	MH05
SF36209I	SF-36 v2.0 Standard-Question 9i	VT04
SF36210	SF-36 v2.0 Standard-Question 10	SF02

SF36211A	SF-36 v2.0 Standard-Question 11a	GH02
SF36211B	SF-36 v2.0 Standard-Question 11b	GH03
SF36211C	SF-36 v2.0 Standard-Question 11c	GH04
SF36211D	SF-36 v2.0 Standard-Question 11d	GH05

The normative score and the 0-100 scale score for individual domain, along with the normative score for PCS and MCS will be exported from PRO CORE. The exported code and the corresponding ADaM parameter code and descriptions are outlined below.

Outputed Parameter Code	Parameter Code in ADaM	Parameter Description in ADaM
BP	BP	Bodily Pain 0-100 Score
GH	GH	General Health 0-100 Score
MH	MH	Mental Health 0-100 Score
PF	PF	Physical Functioning 0-100 Score
RE	RE	Role-Emotional 0-100 Score
RP	RP	Role-Physical 0-100 Score
SF	SF	Social Functioning 0-100 Score
VT	VT	Vitality 0-100 Score
BP_NBS	BPT	Bodily Pain Normative Score
GH_NBS	GHT	General Health Normative Score
MH_NBS	MHT	General Health Normative Score
PF_NBS	PFT	Physical Functioning Normative Score
RE_NBS	RET	Role-Emotional Normative Score
RP_NBS	RPT	Role-Physical Normative Score
SF_NBS	SFT	Social Functioning Normative Score
VT_NBS	VTT	Vitality Normative Score
MCS	MCST	Normative Mental Component Summary Score
PCS	PCST	Normative Physical Component Summary Score

Descriptive statistics will be performed based on normative scores.

In addition, there is no transformation of item Health Transition. Analysis of Health Transition will be based on the original results.

6.14.2.2. ADaM domain generation

For combined analysis, only the composite score is stored in the ADaM dataset. The original SF-36 questionnaires will be kept in SDTM only.

6.14.2.3. Handling of duplicate entries on Questionnaire form for SF-36 scoring

For SF-36 scoring, unique assessment per subject per question item per day is required. In case a subject have duplicate entries within the same day for a question item, the following handling rules will be applied:

- If a respondent marks two responses which are adjacent to each other, then the worst case (lowest value) is selected. For questions BP01, BP02, GH01, GH03, GH05, VT01, VT02, SF01, MH03 and MH05, the record with higher score is considered "worst case". For other questions the record with lower score is considered "worst case".
- If a respondent marks two responses which are not adjacent to each other, then the score is missing for that item.
- If a respondent marks three or more responses then the score is missing for that item.

6.14.2.4. Selection of subset population for dry-run SF-36 scoring

Due to limited administrations licensed at PRO CORE, a subset of data from internal SDTM data (dated 30Oct2023) will be selected for Dry-run. The selection rules are outlined below:

- 1. To select subjects who have completed the study or subjects who have reached visit "Week 240".
- 2. To check SF-36 assessments for these subjects and exclude subjects with multiple assessments within the same date.
- 3. To include all assessments at any visits for the selected subjects for SF-36 scoring for Dryrun.
- 4. To keep subjects who have completed the study prior to 31-12-2022 or who have visit "Week 240".
- 5. In order to perform visit remapping for EOT visit of subjects who prematurely discontinue the study. The SF-36 assessments of the first 10 subjects who had discontinued the study are added for Dry-run analysis.

This results to approximately 1000 assessments to be included for Dry-run.

